5 STUDY EVALUATIONS AND MEASUREMENTS

5.1 Screening and Monitoring Evaluations and Measurements

5.1.1 Medical Record Review

Include a listing of the variables that will be abstracted from the medical chart (paper or electronic).

- Date of birth
- Zip code
- Race and ethnicity

- Medical history
- Surgical history
- Height and weight
- Medications history

Sleep study if performed in the last 3 months

5.1.2 History and Physical Examination

A structured history and examination will include:

- Asthma presence and severity
- Atopy
- Eczema
- Rhinitis
- Symptoms of OSAS
- Examination of the nares
- Clinical tonsillar size (0 - 4+)
- Visual oral airway patency using the modified Mallampati scale
- Standing height will be measured with a stadiometer (Holtain, Crymych, UK)
- Weight will be measured on a calibrated digital electronic scale
- Body mass index z-scores will be calculated
- **Ocular health:** Ophthalmologic exam including standardized measurement of recognition acuity, slit lamp examination to detect cataract, intraocular pressure measurement using i-Care tonometry, and a dilated fundus examination, performed by the CHPS Ophthalmology Core.

5.1.3 Vital Signs

Pulse and BP will be measured after the subject has been seated quietly for 10 minutes. For BP, systolic and diastolic BP will be measured once, using automated equipment, according to standardized guidelines. Cuff size will be determined by measuring the circumference of the upper arm, measured at the midpoint, and identifying the appropriate bladder size from a standard chart.

5.1.4 Laboratory Evaluations

Blood sampling will be performed for the following laboratory evaluations

- Systemic Biomarkers

5.1.4.1 *Systemic Biomarkers*

Systemic markers of atopy (serum IL-4 and IL-13) and systemic (serum TNF α and hsCRP) inflammation in response to NCS will be measured at baseline and 3 months from blood.

IL-4, IL-13 and TNF α will be measured using a multiplex kit manufactured by Meso Scale Discovery (Rockville, MD) on an MSD Sector 6000 Imager. MSD assays are well known for its wide dynamic range and high signal-to-noise ratios(38).

High sensitivity C-reactive protein (hsCRP) will be measured using a laser-based immunonephelometric method on the BNII (Siemens Healthcare Diagnostics, Deerfield, IL). Limits of detection for hsCRP are 0.16 mg/L, while total imprecision for hsCRP assays range from 2.1-5.7%.

5 mL of blood total will be required to run these tests. Samples will be drawn by pediatric CHPS nurses and will be labeled using participants study ID numbers. Tests will be performed in the CHPS Center for Human Phenomic Science (CHPS).

5.1.4.2 *Urine pregnancy test*

Female participants ages 10 and older or those who have attained menarche will be asked to provide a urine sample for pregnancy testing prior to the whole body DXA scan. Positive pregnancy results will be shared with the subject and not with the parent(s). Subjects will be encouraged to share the results with their parent (s). If desired by the subject, the CHOP pulmonary social worker will be consulted. Pregnant females will be excluded from the study.

5.1.5 *Other Evaluations, Measures*

- **Baseline Polysomnography:**

Overnight polysomnography will be performed in the pediatric sleep laboratory. The following parameters will be recorded (using Rembrandt, Medcare, Buffalo, NY): electroencephalogram, electrooculogram, submental and tibial electromyograms, chest and abdominal wall movement by inductance plethysmography (Respitrace, Ambulatory Monitoring Inc., Ardsley, NY); ECG; airflow by nasal pressure (Pro-Tech, Mukilteo, WA) and 3-pronged thermistor (Pro-Tech), end-tidal PCO₂ (Novametrix 7000; Novametrix, Wallingford, CT); arterial oxygen saturation and digital, infra-red video. The infra-red video is a component of any sleep study that is crucial for polysomnography interpretation as it provides information on breathing patterns, parasomnias, movements and seizures. The following parameters will be determined using standard pediatric techniques and scoring: (39)

1. Sleep architecture
2. Apneas and hypopneas
3. Arterial oxygen saturation (S_pO₂)
5. End-tidal carbon dioxide tension (ETCO₂)

- **Neurocognitive and Behavioral measures** (the neurocognitive measures in non-English/Spanish speaking participants will be omitted unless a validated interpreted version is commercially available.):
 - The Epworth Sleepiness Scale modified for children
 - The Child Behavior Checklist (CBCL)(40)
 - Behavior Rating Inventory of Executive Function (BRIEF)
 - Conners Abbreviated Symptom Questionnaire
 - Conners Kiddie Continuous Performance Test Version 5 (K-CPT) for children aged 5 years and the Conners Continuous Performance Test (CPT-II) for children older than 5 years. Purdue Pegboard, a widely used test of fine motor coordination
- **Airway size measurement:**
 - Airway size will be measured using acoustic reflectance (Eccovision, Hollywood, FL), a noninvasive clinical technique which has been used successfully in children in order to measure both the nasopharyngeal and oropharyngeal airway diameter. This device has been used previously for research protocols (IRB #9752) and has been approved by the device committee. The participant wears nose clips and breathes into a mouthpiece for a few minutes.
- **OSAS symptoms:**
 - The Pediatric Sleep Questionnaire (PSQ) will be used
- **Nasal symptoms will be measured by the following questionnaires:**
 - Nasal Obstruction Symptom Evaluation (NOSE) scale, a validated scale of nasal obstructive symptoms (41), modified by deleting the question about sleep and written in child-friendly language.
- **Quality of life** (the Quality of Life measures in non-English/Spanish speaking participants will be omitted unless a validated interpreted version is commercially available:
 - Pediatric Quality of Life Inventory (PedsQL), a well-validated, generic measure of global quality of life
 - The OSAS-18 will be used as a disease-specific pediatric quality of life measure (42, 43).
 - Paediatric Rhinoconjunctivitis Quality of Life Questionnaire, a validated measure of rhinitis-specific quality of life.

Spirometry: Standard spirometry will be performed.

- **Allergy testing:** Percutaneous skin testing will be performed on the forearm with a bifurcated needle (Allergy Labs of Ohio, Columbus, Ohio) by pricking through a drop of the extract, which is then absorbed. The allergens will be commercial extracts (Greer Laboratories, Lenoir, NC) representative of local allergens in the greater Philadelphia area (44), including *Der P*, *Der F* (dust mite), *Fel d I* (cat), *Can f1* (dog), *Acer* (maple), *Quercus* (Oak), *Betula* (Birch), Poaceae (grass), *Ambrosia* (ragweed), and *Rumex* (dock sorrel). Reactions will be recorded by measuring the largest diameter of the wheal-and-flare response in millimeters at 15 minutes. The test result will be considered positive if the wheal is 3 mm larger than that elicited by the negative control.
- **Nasal Biomarkers:** Nasal markers of atopy (nasal IL-4 and IL-13) and local (fractional exhaled nitric oxide [FeNO], nasal TNF α) inflammation in response to NCS will be measured at baseline and 3 months from a nasal swab. Samples will be labeled using the participants study ID number and tests will be performed in the CHPS Center for Human Phenomic Science (CHPS), except for FeNO that will be performed in the Pulmonary Core Lab.
 - IL-4, IL-13 and TNF α will be measured using a multiplex kit manufactured by Meso Scale Discovery (Rockville, MD) on an MSD Sector 6000 Imager. MSD assays are well known for measuring cytokines from nasal secretion using a multiplex immunoassay.
 - FeNO will be measured with a portable device (NIOX MINO, Aerocrine, Morrisville, NC) that has been validated against chemiluminescence (45).
- **Genetic markers:** Whole genome expression profiles from upper airway cells to identify individuals with a Th2-high phenotype will be generated. RNA will be extracted from nasal brushings and assayed on Illumina's HumanHT-12 v4 Expression BeadChip which contains over 47,000 probes derived from the National Center for Biotechnology Information Reference Sequence (NCBI) RefSeq Release 38. Following data normalization and summarization using Robust Multi-Array Average expression measures (RMA) samples will be grouped by Th2 status using cluster analysis of IL-13 induced genes as previously described (32). Samples will be labeled using the participants study ID number and will be performed in the Center for Applied Genomics by co-investigator [name].
- **Growth:** Knee height assessment for short-term growth evaluation will be obtained using a high precision (0.01 mm) knee height measuring device (Marine Computer Tech Inc., Chadds Ford, PA) that measures lower leg length from the heel to the superior surface of the knee (46). This highly accurate device is able to detect significant growth of the lower leg in 6-8 weeks. This will be performed in the CHPS Nutrition Core.

- **Bone health:** Dual Energy X-ray Absorptiometry (DXA) is the most commonly used technique for clinical diagnosis of low bone mass in children. Female participants ages 10 and older or those who have attained menarche will be asked to provide a urine sample for pregnancy testing prior to the whole body DXA scan. Pregnant females will be excluded. Bone mineral density of the lumbar spine and whole body are the recommended measurement sites for bone density assessment in children (47). They will be assessed using a Hologic Discovery bone densitometer (Hologic, Bedford, MA) operating in Apex software version 3.3. The *in vitro* coefficient of variation is < 1% and the *in vivo* coefficient in children is < 2%. This will be performed in the CHPS Nutrition Core.
- **Adrenal suppression:**
 - Morning cortisol: Assays will be measured by a solid-phase, two-site sequential chemiluminescent immunometric assay run on an automated Siemens Immulite 1000 clinical analyzer according to the manufacturer's specifications.
 - Adrenocorticotropic hormone: Assays will be measured by a solid-phase, two-site sequential chemiluminescent immunometric assay run on an automated Siemens Immulite 1000 clinical analyzer according to the manufacturer's specifications. Blood will be collected into iced EDTA tubes and centrifuged at 4°C.
 - DHEAS
- **Infection:** Families will keep a log of all infections and illnesses.

5.2 Efficacy Evaluations

5.2.1 Diagnostic Tests, Scales, Measures, etc.

The **primary objective** of this study, the change in AHI 3 months after randomization, will be measured by baseline polysomnography.

The following measures will be used to determine which factors modify the response to NCS and the side-effects associated with chronic NCS use in children with OSAS of this study 3 months after randomization:

- Cognitive and behavioral measures
- Knee height measurement,
- DXA scan
- Blood work (biomarkers, genetics, cortisol, DHEAS and ACTH)
- Ophthalmology evaluation

- OSAS symptoms questionnaires
- Nasal symptoms questionnaires
- Quality of life questionnaires
- Airway size measurement
- Spirometry
- Percutaneous skin allergy test

These measurements will be performed at the CHPS.

The following measures will be used to determine which factors modify the response to NCS, the side-effects associated with chronic NCS use in children with OSAS of this study, and the long-term effect of NCS vs. placebo in the treatment of OSAS in children 12 months after randomization:

- Sleep study
- Knee height measurement
- DXA scan
- Blood work (biomarkers, genetics, and cortisol, DHEAS, ACTH levels),
- Ophthalmology evaluation
- OSAS symptoms questionnaires
- Nasal symptoms questionnaires
- Quality of life questionnaires
- Airway size measurement
- Cognitive and behavioral measures
- Spirometry
- Percutaneous skin allergy test

These measurements will be performed in the CHPS.

5.3 Pharmacokinetic Evaluation

N/A

5.4 Safety Evaluation

Subject safety will be monitored by adverse events, vital signs, physical examinations (ocular health), sleep study results, laboratory data (cortisol, DHEAS, ACTH), cognitive and behavioral measures, and DXA scan results.

6 STATISTICAL CONSIDERATIONS

6.1 Primary Endpoint

The primary endpoint is the change in AHI at the 3-month visit.

6.2 Secondary Endpoints

Secondary endpoints will include the following:

- The change in AHI at the 3-month visit in each group according to the presence of atopy or obesity.
- The change in AHI at the 12-month visit in each group
- The change in knee height, bone health, adrenal suppression, ocular health and infection at 12 months.

6.3 Statistical Methods

6.3.1 Baseline Data

Baseline and demographic characteristics will be summarized by standard descriptive summaries (e.g. means and standard deviations for continuous variables such as age and percentages for categorical variables such as gender).

6.3.2 Efficacy Analysis

The primary analysis will be based on an intention to treat approach and will include all subjects randomized at Visit 1.

The primary efficacy endpoint will be the change in AHI between Randomization and Visit 2.

Secondary endpoints will include the change in AHI at the 12-month visit in each group and the change in knee height, bone health, adrenal suppression, ocular health and infection at 12 months.

6.3.3 Pharmacokinetic Analysis

N/A

6.3.4 Safety Analysis

All subjects entered into the study at Visit 1 will be included in the safety analysis. The frequencies of AEs by type, body system, severity and relationship to study drug will be summarized. SAEs (if any) will be described in detail.

AE incidence will be summarized along with the corresponding exact binomial 95% two-sided confidence intervals.

6.4 Sample Size and Power

Sample size for primary endpoint:

All sample size calculations were conducted using nQuery Advisor software. It is assumed that 50% of subjects will fail the baseline screening PSG. Thus, 318 subjects will be recruited initially. 159 eligible subjects will be randomized in a 2:1 fashion to NCS *vs* placebo, respectively; the initial group sizes will therefore be 106 NCS *vs* 53 placebo subjects. The 2:1 randomization ratio is to allow for further randomization for Aim 3. Based on our past studies (see *Preliminary Data*), we will assume a drop-out rate of 5% at 3-months. Therefore, the available sample size for the primary endpoint analysis will be 100 NCS *vs* 50 placebo subjects. This is powered on a comparison of mean changes in AHI between NCS *vs* control subjects at 3-months, based on two prior studies (13, 15). The effect-size for the difference in mean changes between treatment groups for the Brouillette study, calculated as the absolute value of the difference in group means, divided by the pooled estimate of the SD of changes, was 0.87 (15), and for the Kheirandish-Gozal study was 1.75.(13) A two group t-test with a 0.050 two-sided significance level will have $\geq 99\%$ power to detect the effect size of 0.865 (observed in (13)) when the sample sizes in the two groups are 100 and 50, respectively. In addition, the two group t-test will also have $>99\%$ power to detect the effect size of 1.75 that was observed in (15). We will therefore have excellent power to determine treatment group differences of the magnitude observed by these past studies. However, as the effect sizes were so different for these two studies, and as the current study will include a more heterogeneous population, e.g., children with more severe OSAS, the observed effect-size may be smaller. If so, we will have 81% power to detect an effect size of 0.50. An effect-size of 0.50 corresponds to a mean reduction in AHI of 4.2/hr in the NCS group and no change in the placebo group, assuming the SD of changes is 8.4 (as observed in (13)); and an AHI reduction of 1/hr with NCS (and no change in placebo) if the SD of change is 2 as observed in (15). Any smaller difference between groups with respect to changes in AHI would not be clinically meaningful. We are therefore well-powered to detect meaningful changes for the primary endpoint.

Sample size for secondary endpoints:

Comparison of the changes in AHI between treatment groups, according to whether or not subjects are atopic or obese: Based on preliminary data from CHAT (4), the proportion of children with asthma/atopy is expected to be $\sim 31\%$ while the proportion who are obese is expected to be $\sim 34\%$. With 100 *vs.* 50 subjects in the NCS and placebo groups, respectively, the number of subjects in each subgroup is expected to be: 31 atopy/NCS, 69 non-atopic/NCS, 15 atopic/placebo, and 35 non-atopic /placebo. The power to test for an interaction was evaluated by constructing a contrast for a one-way comparison of means in nQuery, to test the hypothesis that the difference in mean reduction in AHI between subjects treated with NCS *vs* placebo is equal for subjects with *vs* without atopy. When the total sample size is 150, a 0.050 level two-sided t-test of the specified contrast for an interaction of atopy by treatment in a one-way analysis of variance will have 80% power to detect an effect-size of 0.51 (here the effect-size is calculated as the absolute value of the contrast

mean divided by the within group SD and scale; it represents an index of the size of the contrast). An effect size of 0.51 would be observed if the mean change (post minus pre) in AHI is -6/hr for atopic subjects *vs* -3/hr for non-atopic subjects in the NCS groups, when the changes in AHI are 0/hr for atopic subjects and non-atopic subjects in the placebo group; this also assumes that the SD of changes is 2.8; a simulation program written in Stata based on 10,000 simulated data sets also indicated that we have 80% power to detect a significant treatment group by atopic interaction for this scenario. If similar results are observed for assessment of obesity (mean change in AHI of -6/hr for non-obese subjects *vs* -3/hr for obese subjects in the NCS group, versus 0/hr for obese subjects and non-obese subjects in the placebo group) this will result in an effect-size of 0.503; this assumes that the SD of changes is 2.8 and 34% of children are obese, so that the number of subjects in each subgroup is 34 obese/NCS, 66 non-obese/NCS, 17 obese/placebo, and 33 non-obese/placebo. We will have 82% power to detect an effect size of 0.503. This degree of relative improvement in AHI for NCS *vs* placebo in the atopic *vs* non-atopic and in the obese *vs* non-obese groups is clinically meaningful.

Comparison of the changes in AHI at 12 months: For this endpoint, the 100 remaining NCS subjects (assuming there were ~6 dropouts) at 3-months will be re-randomized in equal numbers to continued NCS or placebo. Assuming a conservative drop-out rate of 10%, there will be 45 evaluable subjects per treatment group at 12 months. We anticipate that subjects treated with NCS will continue to improve (i.e., have continued reductions in AHI), while those on placebo will have a worsening of their condition (i.e., increases in AHI). We anticipate that subjects who continue on NCS will have similar (or greater) improvements during the additional 9 months of follow-up as were observed during the first 3 months of treatment. Assuming that NCS subjects have a mean reduction in AHI of 4/hr, while placebo subjects have a mean increase of 3/hr, a two-sample t-test will have 97% power to detect this difference, assuming that the common SD of changes is 8.4 (as in (15)); if the SD of changes is 2.0 (as in (13)), then we will have >99% power. However, if the observed differences of the current study are smaller, a sample size of 45 in each group will have 80% power to detect an effect size of 0.597; this would be observed if the mean reduction in AHI is 2.4/hr for subjects treated with NCS, *vs* no change for subjects treated with placebo, assuming a SD of 4.0(13).

Side effects of NCS: The proportion of subjects with side-effects will be computed (with 95% CI). The average number of side-effects (with 95% CI) will also be computed. We do not anticipate that there will be an appreciable number of side-effects in either treatment group, but we will have excellent power to detect a meaningful difference between groups. A Fisher's exact test with a 0.050 two-sided significance level will have 84% power to detect the difference between the 50 placebo *vs* 100 NCS subjects at 3 months, if 1% of placebo *vs* 15% of NCS subjects have side-effects at 3 months. For comparison of the 45 treated *vs* 45 placebo subjects during the second 9 months of follow-up, we will have 82% power to detect a difference between 1% *vs* 20% of subjects with side-effects, respectively. In addition, the proportion of the 100 subjects initially randomized to NCS who have side-effects at any time during follow-up will be computed (with 95% CI). An exact binomial test with a nominal 0.050 two-sided significance level will have 85% power to detect an adverse event rate of 6% amongst the 100 NCS subjects at any time during follow-up (*vs* a hypothesized rate of 1%).

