Statistical And Analytic Plan	
 • It is assumed that 50% of subjects will fail the baseline screening PSG. Thus, 318 subjects will be recruited initially. • 159 eligible subjects will be randomized in a 2:1 fashion to NCS vs. placebo, respectively; the initial group sizes will therefore be 106 NCS vs. 53 placebo subjects. The 2:1 randomization ratio is to allow for further randomization during the follow-up phase of the study. Based on our past studies we will assume a drop-out rate of 5% at 3 months. Therefore, the available sample size for analysis for Aim 1 will be 100 NCS vs. 50 placebo subjects. • All analyses will be conducted with Stata 13.0, with two-sided tests of hypotheses and a p-value < 0.05 as the criterion for statistical significance. • Analyses will be conducted according to the intent to treat principle, with subjects analyzed according to their initial treatment assignment. • Descriptive analyses will include computation of means (with 95% confidence intervals), standard deviations, medians, interquartile-ranges (IQR) of continuous variables and tabulation of categorical variables. • A two-group t-test for independent samples or Wilcoxon rank sum test will be used to test the primary hypothesis that

the changes in AHI are equal between the two treatment groups.

[figure not shown]
DATA AND SAFETY MONITORING PLAN

Participants' data will be closely monitored by an external Data Safety Monitoring Board (DSMB) and an external safety officer. They will monitor adverse events and treatment failures.

TABLE 1: SCHEDULE OF STUDY PROCEDURES

Percutaneous skin allergy test		X												
Blood tests		X			X									X
Ophthalmology exam		X			X									X
Nasal secretion testing		X			X									X
DXA scan		X			X									X
Urine pregnancy test		X			X									X
Randomization		X			X									
Dispense Study Drug		X			X									
Drug Compliance					X		X				X			X
Adverse Event Assessment		X	X	X	X	X	X	X	X	X	X	X	X	X

FIGURE 1: STUDY DIAGRAM

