3.1.3 Phase 2: 3-month visit

Participants randomized to both groups will receive monthly phone calls and come back at 3 months for a visit. Sleep study and all procedures performed at the baseline visit, except for physical examination, will be repeated at 3 months. Medication canisters will be weighed. Participants in the placebo group will then be referred to clinical care (for evaluation for further clinical treatment such as surgery if their sleep study is still abnormal, or for routine ongoing clinical surveillance if their sleep study has normalized). Children in the NCS group will be referred to clinical care if their sleep study shows severe OSAS or significant hypoxemia or hypercapnia, such that definitive treatment should not be delayed (AHI $> 30/\text{hr}$, more than 2% total sleep time with SpO₂ $<90\%$, end-tidal PCO₂ $> 60 \text{ mm Hg}$ for > 5 minutes, or pathologic arrhythmias)(4). In addition, children with (i) DXA scans showing spine or whole body bone mineral density < -2.0 standard deviations using race specific curves with adjustment for height Z-score, (ii) ophthalmologic exam showing cataracts or intra-ocular pressure $> 22 \text{ mm Hg}$ on two measurements will be withdrawn from the study and referred to clinical care. Note that DXA results may not be available on the same day, in which case the participant will be randomized, but will later be withdrawn from the study and referred for clinical care if the DXA results are abnormal.

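### The 12-month sample size makes no deduction for the month-3 referrals and withdrawals, so 45 per arm is an upper limit, and the SD behind its detectable difference is inconsistently sourced

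*Combined protocol and SAP*

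**What the plan says.** Section 6.4 builds the 12-month numbers in three steps.

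- At baseline, "the initial group sizes will therefore be 106 NCS", and for the first phase "we will assume a drop-out rate of 5% at 3-months".
- At month 3, "the 100 remaining NCS subjects (assuming there were ~6 dropouts) at 3-months will be re-randomized in equal numbers to continued NCS or placebo".
- From month 3 to month 12, "Assuming a conservative drop-out rate of 10%, there will be 45 evaluable subjects per treatment group at 12 months".

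It then gives 97% power for the main scenario (a fall of 4/hr on NCS against a rise of 3/hr on placebo, SD 8.4). As a fallback for smaller differences it gives 80% power for effect size 0.597, illustrated as 2.4/hr against no change.

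Section 3.1.3 describes who leaves at month 3: "Children in the NCS group will be referred to clinical care if their sleep study shows severe OSAS", with further polysomnographic criteria in the same sentence. It also withdraws children with specified DXA or eye findings. When the DXA result arrives late, the child is randomized first and withdrawn afterwards. Sections 3.1.4 and 4.4 confine the second randomization to NCS children who did not need referral. Both point to 3.1.2 for the criteria, although the month-3 criteria stand in 3.1.3.

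On the SD, the 12-month paragraph says of reference 13: "if the SD of changes is 2.0 (as in (13)), then we will have >99% power". For the fallback it then writes "assuming a SD of 4.0(13", again citing reference 13. The primary-endpoint paragraph of 6.4 credits reference 13 with SD 8.4 and reference 15 with SD 2. The 12-month paragraph reverses that pair.

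Section 3.3.2 expects 100 evaluable children at 12 months.

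**The concern.** The design contains planned exits between the first and second randomization, and the calculation has no line for them. It takes off drop-outs only, so 50 per arm at re-randomization and 45 at month 12 are the most the plan can yield under its own drop-out assumptions. The fallback was set at exactly 80%, so it cannot absorb any loss.

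The 10% later drop-out is called conservative without a reason. It is a lower monthly loss than the plan assumes for the first three months.

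The 2.4/hr figure is what a clinical reader will take as the smallest difference the trial can reliably show at 12 months. It depends entirely on an SD of 4.0, which matches neither SD that the plan says was observed (2.0 and 8.4).

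At stake is the stated sensitivity of the trial's only randomized comparison of continued against stopped treatment. That comparison is a secondary endpoint serving the long-term objective. The side-effect comparison for the same period uses the same 45 against 45.

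**Working it through.** **Inputs from the plan.** Two-sided 0.05 (synopsis: "with two-sided tests of hypotheses and a p-value < 0.05 as the criterion for statistical significance"); 106 NCS children at baseline; 5% lost by month 3; 1:1 re-randomization; 10% lost from month 3 to 12; effect size d = 0.597; main scenario d = 7/8.4 = 0.833.

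**Formula.** With n per arm, power is the probability that a noncentral t variable with 2n - 2 degrees of freedom and noncentrality d x sqrt(n/2) falls outside the central-t 2.5% and 97.5% points.

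**The plan's own figures.** 106 x 0.95 = 100.7, taken as 100, or 50 per arm; 50 x 0.90 = 45.
- n = 45, d = 0.597: power 79.98% (plan: 80%).
- n = 45, d = 0.833: power 97.4% (plan: 97%).

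Both reproduce. There is no arithmetic error given the stated inputs.

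**Adding month-3 exits.** Evaluable n per arm = 50 x (1 - exit share) x (1 - later loss). The documents give no exit share, so 2%, 5% and 10% are assumptions. Two later losses are shown: the plan's 10%, and 14.3% = 1 - 0.95^3, which assumes that the early loss of 5% recurs in each later three-month period.

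| Exits (assumed) | Later loss | n per arm | Power, d = 0.597 | Power, 7/hr with SD 8.4 |
|---|---|---|---|---|
| 0% | 10% (plan) | 45.0 | 80.0% | 97.4% |
| 2% | 10% (plan) | 44.1 | 79.2% | 97.2% |
| 5% | 10% (plan) | 42.8 | 77.9% | 96.8% |
| 10% | 10% (plan) | 40.5 | 75.6% | 95.9% |
| 0% | 14.3% (assumed) | 42.9 | 78.0% | 96.8% |
| 2% | 14.3% (assumed) | 42.0 | 77.2% | 96.5% |
| 5% | 14.3% (assumed) | 40.7 | 75.8% | 96.0% |
| 10% | 14.3% (assumed) | 38.6 | 73.5% | 95.1% |

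At whole numbers, power for d = 0.597 is 78.1% at 43, 75.1% at 40 and 72.9% at 38. The effect size detectable with 80% power is about 0.61 at 43 per arm and 0.65 at 38.

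**Drop-out per month.** First phase: 1 - 0.95^(1/3) = 1.70%. Second phase: 1 - 0.90^(1/9) = 1.16%.

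**Detectable difference by SD at d = 0.597.**
- SD 2.0: 0.597 x 2.0 = 1.2/hr.
- SD 4.0: 0.597 x 4.0 = 2.4/hr (the plan's figure).
- SD 8.4: 0.597 x 8.4 = 5.0/hr.

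With 45 per arm and SD 8.4, a true difference of 2.4/hr would have 27% power.

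**Side effects, second phase.** Fisher's exact test, 1% against 20%: 82% at 45 per arm, as the plan states; 79% at 43, 74% at 40 and 69% at 38.

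**Evaluable total.** 2 x 45 = 90 in section 6.4, against 100 in section 3.3.2. The 100 equals the number re-randomized, before any later loss.

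**The case against.** The strongest reply is that this disputes assumptions and finds no miscalculation. That is right as far as it goes: 45, 80% and 97% all follow from the stated inputs.

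A reader might infer that the plan's own drop-out rate is 5% per three months and that 10% over nine months contradicts it. The documents do not say that. They state 5% once, for the first phase, and a separate 10% for the second. They also describe retention measures: monthly calls, visits 3 and 4, and exclusion of families likely to move or not to comply. A lower later rate is possible; the plan simply does not argue for it.

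A reader might also infer that the design will deliver only 38 per arm. That needs an exit share of about 11% on top of the extrapolated loss (1 - 38/42.9), or about 16% with the plan's 10% (1 - 38/45). Nothing in the documents supports either. They point to few exits: severe disease and abnormal bone or eye findings are screened for at baseline, and section 8.11.2 says steroid effects on bone usually take longer than a few months. Section 8.11.1 reports 1.9% treatment failures in an earlier surgical trial, though by a different criterion. With 2% exits and 10% drop-out, the fallback power is 79%.

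Finally, the 80% belongs to a fallback scenario for a secondary endpoint, and the plan never pairs 2.4/hr with SD 8.4. Both points stand.

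None of this supplies the missing deduction, a reason for the word conservative, or a consistent source for the SD.

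**Conclusion.** The point holds in a limited form. Section 6.4 re-randomizes every NCS child left after drop-out, while sections 3.1.3, 3.1.4 and 4.4 remove some of them, so 45 per arm is a ceiling. Because power there is 79.98%, any exit puts the stated 80% out of reach. The likely shortfall is small: 1 to 4 points for exits of 2-10% with the plan's own drop-out. It reaches about 7 points, at 38 per arm, only if the early drop-out rate also continues. Those exit and continuation rates are assumptions and not properties of the design.

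It would be wrong to conclude that the 12-month comparison is underpowered in general: the main scenario keeps about 95-97% power at 38-43 per arm.

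The SD finding needs no assumption about losses. Section 6.4 credits one reference with 2.0, 4.0 and 8.4, and the detectable difference moves from 1.2 to 5.0/hr accordingly. The conflict between 100 and 90 evaluable children is likewise plain from the text.

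**What to change.** In section 6.4:

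1. Deduct a stated and justified month-3 exit rate before re-randomization. Give evaluable numbers and power as a sensitivity range over exit and drop-out rates, labelled as assumptions. The table under the working can serve as a template; its rates should not be entered as design facts.
2. Report beside that range that the main scenario keeps about 95-97% power.
3. Give a reason for calling 10% conservative, or drop the word.
4. Correct the attribution so that each SD has one verified source, or say plainly that 4.0 is an assumption. Give the detectable difference in events per hour for every SD used.
5. Carry the revised numbers into the 45 against 45 side-effect power.

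Reconcile the 100 evaluable at 12 months in section 3.3.2 with the 90 in section 6.4, and correct the cross-reference to 3.1.2 in sections 3.1.4 and 4.4.

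The cost is restated figures and a slightly less favourable fallback power. The fix needs no extra patients and no change to the design, and the primary endpoint is unaffected.
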